	
equal or above 90 mL/min). The PK and protein binding analysis of telotristat ethyl, its active metabolite (telotristat) and the inactive metabolite LP-951757 will be assessed in eight subjects with severely decreased renal function and compared to those in eight demographically-matched subjects with normal renal function (GFR \geq 90 mL/min) following single oral dose of 250 mg telotristat ethyl. If results of Part A show a substantial effect (set as 2-fold increase in total and unbound of either the maximal plasma concentration (C_{max}) or plasma exposure (AUC) of the active metabolite (telotristat)), the PK and protein binding analysis of telotristat ethyl, its active metabolite (telotristat) and the inactive metabolite LP-951757 will also be assessed in eight subjects with a mildly (GFR between 60 and 89 mL/min, both inclusive) and eight subjects with a moderately (GFR between 30 and 59 mL/min, both inclusive) decreased renal function (Part B) following single oral dose of 250 mg telotristat ethyl. Safety and tolerability of the single oral dose of 250 mg telotristat ethyl will also be evaluated.
 
Renal function will be classified based on estimated GFR as determined by the Modification of Diet in Renal Disease (MDRD) formula.
 
After a maximum 28-day screening period (56 days for subjects with mildly and moderately impaired renal function), eligible subjects will begin their stay at the clinical unit on Day-1 (admission day). Subjects will receive a single oral dose of telotristat etiprate (as one tablet containing 250 mg telotristat ethyl) on Day 1. Following safety assessments, subjects will be discharged from the clinical unit either on Day 2 or Day 4. In the first option (discharge on Day 2), subjects will return to the clinical unit for outpatient visits on Day 3 and Day 4 for PK blood sampling and supply of urine collected at home. In the second option (involving a stay up to Day 4), subjects will have safety assessments performed on Day 2 and will be discharged upon completion of PK blood samplings and urine collection on Day 4. All subjects will return to the clinical unit for an end of study (EOS) visit no less than seven days after dose administration (between Day 8 and Day 15).

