Investigator	Physician responsible for the conduct of a clinical study at a study site. If a study is conducted by a team of individuals at a study site, the investigator is the responsible leader of the team and may be called the principal investigator.
Preliminary (interim) analysis	Any analysis intended at any time prior to the formal completion of a study.
Screen	Act of determining if an individual meets minimum requirements to become part of a pool of potential candidates for participation in a clinical study. In this study, screening involves [invasive or diagnostic procedures and/or tests (for example, diagnostic psychological tests, x-rays, blood draws)]. For this type of screening, informed consent for these screening procedures and/or tests shall be obtained; this consent may be separate from obtaining consent for the study.
Subject	Individual who is or becomes a participant in clinical research, either as a recipient of the test article or as a control. A subject may be either a healthy human or a patient.

Wording Definition

ABBREVIATION

AADC	Aromatic L-amino acid decarboxylase
βHCG	Beta human chorionic gonadotrophin
λ_z	Terminal elimination rate constant
A_e	Amount of unchanged drug excreted in urine
AE	Adverse event
ALP	Alkaline phosphatase
ALT	Alanine aminotransferase
ANOVA	Analysis of variance
APTT	Activated partial thromboplastin time
AST	Aspartate aminotransferase
AUC	Area under the (plasma concentration vs. time) curve
AUC_{0-t_{last}}	Area under the plasma concentration time- curve from time 0 to time t corresponding to the last quantifiable concentration
AUC_{inf}	Area under the (plasma concentration vs. time) curve from time 0 to infinity
AUC_t	Area under the serum concentration time curve from time 0 to last quantifiable timepoint
AUC_{tau}	Area under the (plasma concentration vs. time) curve during dosing interval
AUC_u	Area under the (plasma concentration vs. time) curve unbound
BMI	Body mass index
bpm	Beats per minute
CA	Competent Authority
CFR	Code of Federal Regulations (United States of America)
CI	Confidence interval
CL/F	Apparent total clearance (from plasma)
CLu/F	Apparent total clearance (from plasma) unbound
CL_R	Renal clearance
C_{max}	Observed maximal (peak) concentration
C_{maxu}	Observed maximal (peak) concentration unbound
CRF	Case report form
CRO	Contract research organisation
CRP	C-reactive protein
CRU	Clinical research unit
CS	Clinically significant
CSR	Clinical study report

Wording Definition**ABBREVIATION**

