1.4 Clinical Data

Xermelo® (telotristat etiprate) has a marketing authorisation for the treatment of carcinoid syndrome diarrhoea in combination with SSA therapy in adults inadequately controlled by SSA therapy. Marketing authorisation was based on the results of clinical trials (11) (12) (13) during which over 230 subjects with carcinoid syndrome were treated with telotristat etiprate.

From a PK perspective, telotristat ethyl and its active metabolite (telotristat) have been characterised in healthy volunteers and subjects with carcinoid syndrome. Following oral administration of telotristat etiprate, telotristat ethyl is rapidly absorbed and extensively converted to its active metabolite (telotristat), with some conversion of telotristat to an inactive

metabolite LP-951757 CCI [REDACTED] [REDACTED] [REDACTED] [REDACTED]. Plasma concentrations of telotristat ethyl are significantly lower (approximately 100-fold lower) than those of its active metabolite (telotristat) in both healthy subjects and subjects with carcinoid syndrome at all dose levels investigated during clinical development.

Both telotristat ethyl and its active metabolite (telotristat) are highly bound to human plasma proteins (>99%). During previous investigations on clinical samples from healthy volunteers, the unbound fraction of the telotristat ethyl was below the limit of quantification and could not be assessed, while the unbound fraction of the active metabolite (telotristat) was estimated to be 0.356% (14). The estimated apparent total volume of distribution for telotristat is 296 L in healthy subjects and 231 L in subjects with carcinoid syndrome, which may be suggestive of tissue distribution.

In a [¹⁴C]-telotristat etiprate mass balance study in healthy subjects (15), reported values of cumulative excretion showed that approximately 93% of the administered dose of total radioactivity was recovered in the urine and faeces by the end of sample collection (240 h), with the majority (92.78%) of the dose being recovered from faeces and <1% recovered from the urine.

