2.2 Secondary Objectives

To compare the safety and tolerability of a single oral dose of 250 mg telotristat ethyl in subjects with renal impaired function versus healthy subjects with normal renal function.

To assess the effect of renal impaired function on protein binding of telotristat ethyl and its active metabolite (telotristat).

To evaluate the PK of the inactive metabolite LP-951757 following a single oral dose of 250 mg telotristat ethyl in subjects with renal impaired function and healthy subjects with normal renal function.

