3 INVESTIGATIONAL PLAN

3.1 Overall Study Design and Plan

This will be an open-label single dose staged study starting with a Part A. Part A will include two groups, a test group and a control group. The test group will include eight subjects with a GFR as low as possible (i.e. < 20 mL/min), but not requiring dialysis. If inclusion of such subjects is not possible, subjects with severely decreased renal function (i.e. with a GFR between 15 and 29 mL/min, both inclusive) may be included. The test group will be compared to a control group of eight demographically-matched healthy subjects with normal renal function (i.e. with a GFR equal or above 90 mL/min) (Table 1).

The PK and protein binding of telotristat ethyl and its active metabolite (telotristat) following administration of a single oral dose of 250 mg telotristat ethyl will be evaluated. If the results from Part A of the study show a substantial effect (set as 2-fold increase in either the maximal plasma concentration (C_{max}) or plasma exposure (AUC) of the active metabolite (telotristat), PK and protein binding analysis of telotristat ethyl and its active metabolite (telotristat) will also be assessed in Part B in eight subjects with a mildly and eight with a moderately decreased renal function (see Table 1 for renal function groups definition) following administration of a single oral dose of 250 mg telotristat ethyl. Safety and tolerability of the single oral dose of 250 mg telotristat ethyl will also be evaluated.

After a maximum 28-day screening period (56 days for subjects with mildly and moderately impaired renal function), eligible subjects will begin their stay at the clinical unit on Day-1 (admission day). Subjects will receive a single oral dose of telotristat etiprate (as one tablet containing 250 mg telotristat ethyl) on Day 1. Following safety assessments, subjects will be discharged from the clinical unit either on Day 2 or Day 4. In the first option (discharge on Day 2), subjects will return to the clinical unit for outpatient visits on Day 3 and Day 4 for PK blood sampling and supply of urine collected at home. In the second option (involving a stay up to Day 4), subjects will have safety assessments performed on Day 2 and will be discharged upon completion of PK blood samplings and urine collection on Day 4. All subjects will return to the clinical unit for an end of study (EOS) visit no less than seven days after dose administration (between Day 8 and Day 15).

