11.4.5 Interim Analyses

There will be an interim analysis of PK and safety data following the completion of subjects with severely impaired renal function and demographically-matched healthy subjects with normal renal function (Part A) to determine whether subjects with mildly, and moderately impaired renal function (Part B) will be enroled in the study.

The decision to dose eight subjects with mildly impaired renal function and eight subjects with moderately impaired renal function will be based on the PK evaluation of the Part A subjects and the observation of a 2-fold increase in total and unbound fraction of either the maximal plasma concentration (C_{max}) or plasma exposure (AUC) of the active metabolite telotristat.

Decision will not be based on the PK evaluation of the telotristat ethyl since it is rapidly converted to its active metabolite, but also because its PK profile might not be fully characterised because of anticipated low (or below limit of quantification) plasma concentrations.

This 2-fold increase in total and unbound fraction of either the C_{max} or AUC of the active metabolite (telotristat) in subjects with severely impaired renal function as compared to healthy subjects with normal renal function is a clinically relevant increase and considered as a conservative approach for further PK investigations in subjects with mildly and moderately impaired renal function.

Indeed, in a previous study in healthy subjects (20), 250 mg telotristat etiprate given as a tablet led to a mean maximal plasma concentration (C_{max}) of 449 ng/mL (corresponding to 1.60 ng/mL unbound C_{max} based on an f_u of 0.356%) and a mean plasma exposure (AUC_{inf}) of 1305 h.ng/mL of the active metabolite (telotristat) (corresponding to 4.65 h.ng/mL unbound AUC based on an f_u of 0.356%) (see [Table 2](#) below).

A 2-fold increase in total and unbound fraction of either the mean C_{max} or AUC of the active metabolite (telotristat) would lead to approximately 900 ng/mL (corresponding to 6.40 ng/mL unbound C_{max} based on a 2-fold increase f_u of 0.712%) and 2600 h.ng/mL (corresponding to 18.51 h.ng/mL unbound AUC based on a 2-fold increase f_u of 0.712%) respectively. This mean plasma concentration is close to the one reported following a single oral dose of 1500 mg of telotristat etiprate (given to healthy subjects as six 250-mg tablets) from a previous study (21), while the exposure is below:

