3.1.4 Protein binding endpoints

The unbound concentrations for telotristat ethyl, its active metabolite telotristat (LP-778902) and its inactive metabolite (LP-951757) will be derived at each time point available as follows : $C_u = C_{Total} * \text{mean}(f_u)$, where $\text{mean}(f_u)$ represents the mean of the unbound fractions by timepoint.

The following PK parameters for unbound telotristat ethyl and its active metabolite telotristat (LP-778902) will be calculated using the unbound fraction F_u (defined for each subject as the mean over all time points of the mean of f_u):

- C_{maxu} : Maximum plasma concentration calculated by: $C_{maxu} = C_{max} * F_u$
- AUC_{0-infu} : Area under the concentration-time curve unbound from 0 to infinity calculated by: $AUC_{0-infu} = AUC_{0-inf} * F_u$
- $AUC_{0-tlastu}$: AUC from 0 to the last quantifiable unbound concentration calculated by: $AUC_{0-tlastu} = AUC_{0-tlast} * F_u$
- CL_u/F : Apparent total clearance from plasma calculated by: $CL_u/F = CL/F * F_u$
- V_{zu}/F : Apparent volume of distribution calculated by: $V_{zu}/F = V_z/F * F_u$.

For C_{maxu} and AUC_u , the following MR (normalized and not normalized) will also be calculated:

- $MRC_{maxu} = (C_{maxu} \text{ LP-778902}) / (C_{maxu} \text{ telotristat ethyl})$
- $MRC_{maxuNorm} = (C_{maxu} \text{ LP-778902/Molecular weight(MW)}_{LP-778902}) / (C_{maxu} \text{ telotristat ethyl/MW}_{telotristat ethyl})$
- $MRAUC_{0-infu} = (AUC_{0-infu} \text{ LP-778902}) / (AUC_{0-infu} \text{ telotristat ethyl})$
- $MRAUC_{0-infuNorm} = (AUC_{0-infu} \text{ LP-778902/MW}_{LP-778902}) / (AUC_{0-infu} \text{ telotristat ethyl/MW}_{telotristat ethyl})$
- $MRAUC_{0-tlastu} = (AUC_{0-tlastu} \text{ LP-778902}) / (AUC_{0-tlastu} \text{ telotristat ethyl})$
- $MRAUC_{0-tlastuNorm} = (AUC_{0-tlastu} \text{ LP-778902/MW}_{LP-778902}) / (AUC_{0-tlastu} \text{ telotristat ethyl/MW}_{telotristat ethyl})$
- $MRC_{maxuTotal} = (C_{maxu} \text{ LP-778902}) / (C_{maxu} \text{ LP-778902} + C_{maxu} \text{ telotristat ethyl})$
- $MRC_{maxuTotalNorm} = (C_{maxu} \text{ LP-778902/MW}_{LP-778902}) / (C_{maxu} \text{ LP-778902/MW}_{LP-778902} + C_{maxu} \text{ telotristat ethyl/MW}_{telotristat ethyl})$
- $MRAUC_{0-infuTotal} = (AUC_{0-infu} \text{ LP-778902}) / (AUC_{0-infu} \text{ LP-778902} + AUC_{0-infu} \text{ telotristat ethyl})$

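### As written, the Part B trigger is not met when unbound telotristat exposure doubles unless total exposure doubles too, so it can miss the binding effect the study sets out to assess.

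*Protocol*

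**What the plan says.** The trigger for Part B is stated in five places.

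- Protocol Synopsis (Study design) and SAP 1.2: "set as 2-fold increase in total and unbound of either the maximal plasma concentration", or AUC, of telotristat.
- Protocol 11.4.5 and SAP 3.2.17: "the observation of a 2-fold increase in total and unbound fraction of either the maximal plasma concentration", or AUC.
- Protocol 3.1: "set as 2-fold increase in either the maximal plasma concentration", or AUC, with no mention of total or unbound.

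In the first four, the choice offered by *either* is between Cmax and AUC, not between total and unbound. Protocol 11.4.5 describes the rule as "considered as a conservative approach for further PK investigations" in the mild and moderate groups.

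On binding, Protocol 1.4 puts telotristat at more than 99% bound and reports that "the unbound fraction of the active metabolite (telotristat) was estimated to be 0.356"%. Protocol 2.2 makes the effect of renal impairment on protein binding a secondary objective. SAP 3.1.4 derives Cmaxu and AUCu by multiplying the total parameter by Fu, "defined for each subject as the mean over all time points of the mean of f_u".

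**The concern.** Total and unbound exposure part company when renal impairment changes binding, and that is when the trigger has most to decide. A rule that needs both to double cannot respond to a rise in unbound exposure alone. It is therefore less sensitive than a rule on either quantity, which sits badly with calling it conservative for further investigation.

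At stake is whether the mild and moderate groups are studied when unbound exposure has at least doubled in the severe group. Protocol 1.5 gives the purpose as supporting dose-adjustment recommendations, with protein binding explicitly included.

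Choosing one of the five existing texts would remove the inconsistency but not this problem, because none of them makes unbound exposure sufficient in so many words.

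**Working it through.** **The plan's own example.** Unbound = total × fu, with the 250 mg tablet means from Protocol Table 2 and fu = 0.356%.

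- Baseline: 449 × 0.00356 = 1.60 ng/mL; 1305 × 0.00356 = 4.65 h.ng/mL. Both match 11.4.5.
- At the trigger: 900 × 0.00712 = 6.41 ng/mL (stated 6.40, which is 4 × 1.60); 2600 × 0.00712 = 18.51 h.ng/mL (as stated).
- Rise in unbound exposure: 6.40/1.60 = 4.0 and 18.51/4.65 = 4.0.

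The example doubles total and also doubles fu. If *unbound fraction* in 11.4.5 and SAP 3.2.17 means fu, the criterion needs about a 4-fold rise in unbound exposure.

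**Which cases meet which statement** (Protocol 3.1 read as total):

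| Total ratio | fu ratio | Unbound ratio | Protocol 3.1 | Synopsis, SAP 1.2 | 11.4.5, SAP 3.2.17 (fraction = fu) |
|---|---|---|---|---|---|
| 1.0 | 2 | 2.0 | no | no | no |
| 1.5 | 2 | 3.0 | no | no | no |
| 1.9 | 2 | 3.8 | no | no | no |
| 2.0 | 1 | 2.0 | yes | yes | no |
| 2.0 | 2 | 4.0 | yes | yes | yes |

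In the first row, unbound Cmax is 449 × 0.00712 = 3.20 ng/mL and unbound AUC is 1305 × 0.00712 = 9.29 h.ng/mL, both doubled.

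**Chance of meeting the criterion.** Inputs from the documents: 8 per group; CV 53.62% (AUCinf) and 55.92% (Cmax) from Table 2. Log SD = √ln(1 + CV²) = 0.503 and 0.522. SE of the log ratio = SD × √(2/8) = 0.251 and 0.261. Assumed, because the documents give no value: correlation of log Cmax and log AUC 0.7-0.9; between-subject log SD of fu 0.1-0.3, independent of total exposure. Also assumed: the observed increase is judged on the geometric mean ratio.

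A hand check with true total ratio 1: P(observed AUC ratio ≥ 2) = 1 − Φ(0.693/0.251) = 0.3%; for Cmax, 1 − Φ(0.693/0.261) = 0.4%. For at least one of them it is 0.4% to 0.7%, for correlations from 1 to 0.

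Simulation, 400,000 replicates per setting, unbound ratio = total ratio × fu ratio:

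| True total / unbound ratio | Total *and* unbound exposure | Total *or* unbound exposure |
|---|---|---|
| 1.0 / 2.0 | about 0.6% | 56-62% |
| 1.25 / 2.5 | about 5% | 82-89% |
| 1.5 / 3.0 | 17-20% | 94-97% |
| 1.0 / 1.0 | 0.3-0.5% | 0.7-1.8% |

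If *unbound fraction* means fu, the present rule gives about 0.3%, 2.5% and 9% in the first three rows.

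**Cost of *or* beyond those assumptions.** With no true effect, *or* opens Part B in 3.6-4.2% of trials at fu log SD 0.5 and in 7-8% at 0.7. With a true 1.25-fold rise in total, fu unchanged and fu log SD 0.3, it opens in 9-10%, against 3-4% under *and*.

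**The case against.** The strongest reply is that the threshold for adding 16 subjects is the sponsor's judgement, and that 11.4.5 anchors it. A 1500 mg single dose was called safe and well tolerated at unbound Cmax 6.47 ng/mL and AUC 44.98 h.ng/mL. Unbound doubling alone reaches 3.20/6.47 = 49% and 9.29/44.98 = 21% of those values. That stands as a tolerability margin. It does not bear on whether the trigger detects a 2-fold unbound change, which is the size of change the plan itself chose.

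Second, the scenario needs more than a binding change. Unbound AUC is bioavailable dose divided by unbound clearance, and total AUC is unbound AUC divided by fu. So total unchanged with unbound doubled needs fu to double and unbound clearance to halve. If fu doubled alone, total AUC would fall, unbound AUC would not rise, and an *or* rule on AUC would not fire either. The documents show neither change, and less than 1% of the dose is recovered in urine (Protocol 1.4). This stands: the percentages are conditional and say nothing about how likely the scenario is.

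Third, a reader might infer that every statement demands total exposure. Four do so expressly. Protocol 3.1 does so only by notation: the abbreviation list defines Cmaxu separately as "Observed maximal (peak) concentration unbound", but Protocol 8 lists the unbound parameters under plain symbols.

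Fourth, a reader might infer that the study would close and the dose question go unanswered. The documents do not support that. A data review committee decides, under a charter outside the documents (Protocol 3.1.1). The severe group's unbound ratios would still be reported if the data permit (SAP 3.1.7 and 3.2.2.4.3). Protocol 1.4 also reports comparable telotristat exposure in normal, mild and moderate impairment, although that account does not separate unbound exposure.

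**Conclusion.** The point holds as a statement about the written criterion. Four of five statements require total and unbound together, the fifth reads as total, and none says that unbound exposure alone is enough. If *unbound fraction* is taken as the worked example takes it, unbound exposure must rise about 4-fold. Calling this conservative does not fit: requiring both conditions can only lower the chance of going on to Part B.

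The size is large if fu doubles: about 0.6% against 56-62% when total is unchanged, and still 17-20% against 94-97% when total rises 1.5-fold. These figures rest on lognormal data, the Table 2 CVs, and the assumed correlation and fu variability. The conclusion goes no further than that the criterion would not be met; what the committee would then do is not known.

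**What to change.** Reconcile the Synopsis, Protocol 3.1 and 11.4.5, and SAP 1.2 and 3.2.17 to one trigger that keeps the stated 2-fold threshold: a severe/normal geometric mean ratio of at least 2 for telotristat Cmax or AUC, on total *or* unbound exposure, using Cmaxu and AUCu from SAP 3.1.4. Replace *unbound fraction* with *unbound exposure*, and bring the worked example in 11.4.5 into line. If the conjunction is intended, justify it and drop the word conservative.

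The change is to wording only. The binding samples, the unbound parameters and, if the data permit, their group comparison are already planned for Part A. The price is a higher chance of enrolling 16 Part B subjects without need: with no true effect, about 1-2% instead of 0.3-0.5% for fu log SD up to 0.3, and more if fu is more variable, as shown in the working. The sponsor can narrow that range if it holds between-subject data on fu.

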12 DATA HANDLING AND RECORD KEEPING

12.1 Data Collection

In compliance with GCP, source data, e.g. medical records/medical notes, should be clearly marked and permit easy identification of a subject's participation in the specified clinical study.

Source data identification and location, whether standalone documents or direct CRF records, will be specified in a stand-alone document signed by the investigator(s).

The investigator must record all data relating to protocol procedures, study drug administration, laboratory data, safety and PK data on the source documents and report requested data on electronic CRFs (eCRF) provided for the study (see [Section 12.2](#)).

To ensure accurate, complete, and reliable data, the sponsor or its representative will provide instructional material to the study site(s), as appropriate. Training session will be given during a start-up/initiation meeting for instructions on the completion/data entry of any source data documents and CRF.

The investigators or their designees must verify that all data entries in the CRF are accurate and consistent with Source data records. If certain information is not available for a particular timepoint and/or subject, specific instructions should be followed, e.g. to document that the procedure was either not done or not applicable.

